9.6 SAS, AIMS, and BARS

The mean change from baseline to every trial visit in the double-blind treatment period obtained from the SAS total score, AIMS total score (total of the first 7 item scores), and the BARS Global Clinical Assessment will be tabulated and analyzed using ANCOVA. Analyses will be performed on the OC data set. In addition, analyses will be performed using the maximum (i.e. the worst) value observed during the double-blind treatment period and the last visit data to determine the change from baseline score. The ANCOVA model for the OC data set will include the baseline measure and the treatment group. The ANCOVA model for change at the last visit and for change to the maximum value will include the baseline measure, study center and treatment group. The same analyses will be performed on the AIMS individual item scores 8, 9, and 10. In addition, incidence of BARS Global Clinical

Assessment of Akathisia during the double-blind treatment period by severity category will be provided. Analyses of these EPS rating scales will be performed for the Safety Sample.

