1.3 Schedule of Assessments

					Vi	isit				
				Dou	ıble-Blind T		Period			
					12 v	veeks				Post-
	Screening ^a (Day -21 to Day -1)	Day 0	Week 1 ^b	Week 2	Week 4	Week 6	Week 8	Week 10	End of treatment (Week 12) or ET ^c	treatment Follow-up (21 ± 2 days) ^d
Assessment						± 2 days				
ENTRANCE and HISTORY										
Informed consent	X									
Inclusion and exclusion criteria	X	X								
Confirmation of eligibility	X ^e									
Demography	X									
Medical history	X									
Psychiatric history, including BPD history	X									
Confirm use/no use of ADTs	X									
SCID-5-PD ^f	X									
Diagnostic for concurrent excluded diseases (MINI for Psychotic Disorders)	X									
Prior medication washout ^g	X									
HIV, HBsAg, and anti-HCV	X									
EFFICACY										
ZAN-BPD	X	X	X	X	X	X	X	X	X	
CGI-S		X	X	X	X	X	X	X	X	
CGI-I			X	X	X	X	X	X	X	
PGI-S		X	X	X	X	X	X	X	X	
PGI-C			X	X	X	X	X	X	X	
		X	X	X	X	X	X	X	X	

Table 1.3-1 Sched	ule of Assess	ments									
	Visit										
		Double-Blind Treatment Period									
		12 weeks							1	Post-	
	Screening ^a (Day -21 to	D 0	Week 1 ^b	W. L. 2	W I. 4	Wald	W. J. O.	W1.10	End of treatment (Week 12) or ET ^c	treatment Follow-up $(21 \pm 2$ $days)^d$	
Assessment	Day -1)	Day 0	Week 1	Week 2	Week 4	Week 6 ± 2 days	Week 8	Week 10	OFEI	uays)	
Assessment		X				± 2 days			X		
_		X	X		X	X		X	X		
SAFETY		- 11	21		71	21	I	11	11		
Physical examination ^h	X								X		
Vital signs ⁱ	X	X	X	X	X	X	X	X	X		
Clinical laboratory tests (hematology, serum chemistry, and urinalysis)	x ^j					X			X		
Prolactin (blinded)	X								X		
TSH with reflex to free T ₄ if abnormal	X										
HbA1c	X								X		
ECG^k	X								X		
Urine pregnancy test (FOCBP only) ¹	X	X			X		X		X		
Urine drug screen and blood alcohol test ^m	X					X			X		
C-SSRS ⁿ	X	X	X	X	X	X	X	X	X		
Extrapyramidal symptoms scales (SAS, AIMS, and BARS)		X				X			X		
Adverse events ⁰	X	X	X	X	X	X	X	X	X	X	
Concomitant therapy ^p	X	X	X	X	X	X	X	X	X	X	

Table 1.3-1 Schedu	ıle of Assess	ments								
		Visit								
		Double-Blind Treatment Period								
		12 weeks								
			End of							
	Screeninga								treatment	Follow-up
	(Day -21 to								(Week 12)	(21 ± 2)
	Day -1)	Day 0	Week 1 ^b	Week 2	Week 4	Week 6	Week 8	Week 10	or ET ^c	days) ^d
Assessment						± 2 days				
PHARMACOKINETIC AND PH	IARMACOGI	ENOMIC	SAMPLING	j				T		
Pharmacokinetic sampling ^q						X			X	
		X								
		X								
OTHER PROCEDURES										
IMP dispensing ^S		X^{t}	X	X	X	X	X	X		

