IMP accountability			X	X	X	X	X	X	X	
Schedule optional phone contact/other communication				X ^u						

anti-HCV = antibodies to hepatitis C virus; CCI

; ET = Early Termination;

FOCBP = females of childbearing potential; HBsAg = hepatitis B surface antigen; HIV = human immunodeficiency virus; IRE = immediately reported events; PGI-C = Patient's Global Impression of Change; PGI-S = Patient's Global Impression of Severity; PK = pharmacokinetic;

 T_4 = thyroxine.

^aExtension of screening may be requested and discussed with the medical monitor prior to the expiration of the screening period. Screening visit may be split over two days.

^bWeek designations correspond to the end of the week (eg, Week 4 visit occurs at the end of week 4 of the trial).

^cIf a subject discontinues early, every effort should be made to complete the "Week 12/End of treatment/ET" evaluations as soon as possible and, whenever possible, prior to starting any new medication or treatment.

^dTelephone contact or clinic visit (investigator's discretion) for evaluation of safety (AEs) for all subjects who do not enroll in the open-label extension trial.

^eAn assessment of all inclusion and exclusion criteria will be made to determine the subject's eligibility for the trial CCI . Subjects cannot be enrolled until site personnel have received the final CCI notification from the Medical Monitor or Clinical Scientist.

- ^fThe BPD and antisocial personality disorder modules must be conducted as part of screening in order to meet inclusion/exclusion criteria; however, per investigator discretion other PD modules may be administered at baseline in order to decrease the length of the screening visit. The investigator is responsible for determining that BPD is the primary personality disorder diagnosis at screening.
- ^gWashout of prohibited medications begins after completion of the consent process and must comply with the required washout periods (see Section 6.5).
- ^hTo include measurement of height (at screening only) and waist circumference.
- ¹Vital sign measurements include body weight, body temperature, systolic and diastolic blood pressure, and heart rate. Blood pressure and heart rate will be measured in the following order: supine and standing after the subject has been in each position for at least 3 minutes. Vital signs scheduled for the same visit as blood samples are to be completed before blood is drawn.

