5.2 Handling of Missing Data

In general, missing data will be handled by analysis of mixed-effect model repeated measures (MMRM) methodology based on observed-case (OC) data from protocol-specified visits under the assumption of missing at random (MAR). The OC dataset consists of actual observations recorded at each visit and no missing data will be imputed.

The last observation carried forward (LOCF) analysis will include data recorded at a scheduled double-blind treatment phase visit or, if no observation is recorded at that visit, data carried forward from the previous scheduled double-blind treatment phase visit. Baseline data will not be carried forward to impute missing values for the LOCF analysis.

6 Study Conduct

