10.1 Study Visit Windows

Study visit windows will be used to map visits using study day intervals. Observations at each scheduled visit and Early Termination will be assigned to Week 1, Week 2, Week 4, Week 6, Week 8, Week 10 and Week 12 visits based on their visit windows as shown in Table 10.1A. This visit window convention applies to tables and listings for all efficacy and safety scales (ZAN-BPD, CGI-S, CGI-I, PGI-S, PGI-C, SAS, AIMS and BARS). This derived study window variable will be named as DAY and will be footnoted. In listings, it will be listed along with the CRF study visit.

Table 10.1A shows classifications for study day intervals in the double-blind period. The variable "target day" is defined using the number of days since the start of double-blind dosing. The first day of double-blind dosing is defined as "Day 1".

If more than one observation falls within a particular study day interval, then the last observation within that interval is used. Evaluations occurring more than 7 days after the last double-blind dosing date will not be mapped into study visit windows, and will be excluded from the analysis.

Table 10.1A: Study Day and Visit Windows

Week	Target Day ^a	Study Day Interval ^a
2	7	2-13
4	21	14-27
6	35	28-41
8	49	42-55
10	63	56-69

12	77	70-84 ^b

^a Relative to the first day of IMP in the double-blind treatment period.

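### SAP 9.6 plans observed-case ANCOVAs of SAS, AIMS and BARS at every double-blind visit, but the scales are scheduled only at Day 0, Week 6 and Week 12/ET, so the Week 2, 4, 8 and 10 rows would hold almost only early terminators

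*SAP*

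**What the plan says.** - **What is analysed.** SAP 9.6 covers "The mean change from baseline to every trial visit in the double-blind treatment period obtained from the SAS total score, AIMS total score" and the BARS global assessment, and applies the same analyses to AIMS items 8, 9 and 10. It adds "Analyses will be performed on the OC data set" and "The ANCOVA model for the OC data set will include the baseline measure and the treatment group".
- **What observed case means.** SAP 5.2: "The OC dataset consists of actual observations recorded at each visit and no missing data will be imputed".
- **When the scales are rated.** In the Protocol 1.3 schedule, the row "Extrapyramidal symptoms scales (SAS, AIMS, and BARS" is marked only at Day 0, Week 6 and Week 12/ET. The cells for Weeks 1, 2, 4, 8 and 10 are empty. Footnote c asks that early discontinuers complete the full Week 12/ET evaluations, so the scales are also rated when a subject stops.
- **Where ET ratings go.** SAP 10.1: "Observations at each scheduled visit and Early Termination will be assigned to Week 1, Week 2, Week 4" and the later visits, by study day. The scales covered are listed as "ZAN-BPD, CGI-S, CGI-I, PGI-S, PGI-C, SAS, AIMS and BARS". If several observations fall in one window, the last is used. Evaluations more than 7 days after the last double-blind dose are not mapped.

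**The concern.** Each rule is ordinary on its own. Together they order treatment comparisons at four time points where nobody still in the trial is due to be rated. The observed cases at Weeks 2, 4, 8 and 10 would be subjects whose ET visit fell in that window, plus any stray off-schedule rating.

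Membership of such a row is decided after randomisation, by stopping, so its between-arm difference is not a randomised comparison. The by-visit profile would also alternate between nearly the whole Safety Sample (Weeks 6 and 12) and a handful of dropouts (the other weeks), and could be misread as a time course.

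A smaller version of the problem arises at Week 6. An ET rating in that window is pooled with the scheduled ratings. Under the last-observation rule it can replace the same subject's scheduled rating.

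**Working it through.** The plan states no figure for these rows, so there is none to reproduce. The two figures borrowed to size the problem, 240 randomised (120 per arm) and 5% non-evaluable/dropout, come from SAP Section 4. The calculation there reproduces: 2 × (1.96 + 0.842)² × 6.5² / 2.6² = 98.1, so 99 per arm against the stated 100, and power at 100 per arm is 0.807.

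**Step 1: do scheduled visits spill into neighbouring windows?** SAP 5.1 and 7.1 place the first double-blind dose at the Week 1 visit, and Table 10.1A counts days from that dose. Take visit *k* at 7*k* ± 2 days from Day 0, the first double-blind dose at 7 ± 2, and call the dosing day Day 1.
- Week 6: 42 − 7 ± 4 + 1 = days 32 to 40, inside the 28–41 window.
- Week 12: 84 − 7 ± 4 + 1 = days 74 to 82, inside the 70–84 window.

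Visits within tolerance therefore put no rating into the Week 4, 8 or 10 windows.

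**Step 2: how many models are affected?** Six outcomes (SAS total, AIMS total, BARS global, AIMS items 8, 9 and 10) × 6 windows (Weeks 2, 4, 6, 8, 10, 12) = 36 observed-case ANCOVAs. Of these, 6 × 4 = 24 fall where nothing is scheduled and 12 fall at Weeks 6 and 12.

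**Step 3: how many subjects per row?** Assume all 240 are dosed and every ET rating is mapped.
- Even split: 240 × rate / (2 arms × 6 windows).
- Split by window length, with stopping uniform over double-blind days 2 to 77 (76 days): 240 × rate × days / 76. The Week 2 window has 12 days; Weeks 4, 8 and 10 have 14 each.
- Week 6 row: 240 less those who stopped in the Week 2 and Week 4 windows (26 of 76 days).

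**Step 4: can the model be fitted?** Intercept, baseline and treatment are 3 parameters, so at least 4 subjects, with both arms represented, are needed for 1 residual degree of freedom. The chance uses independent binomial counts, 120 per arm.

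| Early-termination rate | ET in all | Per arm per window, even split | Both arms, by window length: Week 2; Weeks 4, 8, 10 | Chance the ANCOVA can be fitted: Week 2; Weeks 4, 8, 10 | Week 6 row, both arms |
|---|---|---|---|---|---|
| 5% (SAP figure) | 12 | 1 | 1.9; 2.2 | 0.11; 0.17 | 236 |
| 10% (assumed) | 24 | 2 | 3.8; 4.4 | 0.49; 0.61 | 232 |
| 20% (assumed) | 48 | 4 | 7.6; 8.8 | 0.92; 0.96 | 224 |
| 30% (assumed) | 72 | 6 | 11.4; 13.3 | 0.99; 1.00 | 215 |

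Example at 5%: 12 × 12/76 = 1.9, 12 × 14/76 = 2.2, and 240 − 12 × 26/76 = 236.

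**Step 5: mixing at Week 6.** The Week 6 window also has 14 days, so 2.2 of about 236 ratings (0.9%) would be ET ratings at 5%, and 13.3 of about 215 (6.2%) at 30%.

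**The case against.** **The phrase may mean every visit at which the scale is collected.** That is a natural reading, but SAP 9.6 does not state it. The SAP names visits when it means to: SAP 9.5.1 analyses waist circumference from screening to Week 12 only. Even on this reading, SAP 10.1 still sends ET ratings to the other windows, so the wording needs repair either way.

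**The displays may be narrower than the text.** SAP Section 13 (list of summary tables) and the COVID-19 addendum are not in the text available here, and either could limit the EPS visits. This stands as a caution. Nothing visible limits them.

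**The consequence is small.** Most of this stands. These are safety analyses outside the four-step hierarchy in SAP 8.3, and Protocol 9.4.2.5 plans only descriptive statistics for them. At 5% most of the affected models could not be fitted, so the likelier result is an empty cell and not a misleading estimate. SAP 9.6 also analyses the last visit, the maximum value and BARS severity incidence, and SAP 9.1 summarises EPS adverse events in five categories.

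**The sizing is approximate.** The 5% is a non-evaluable/dropout rate for the FAS for Enriched Subjects, not an early-termination rate for the Safety Sample. The 7-day rule would lower the counts further. Both points are right, but neither changes who fills the rows.

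**Two stronger inferences are not supported.** A reader might take the 7.2% akathisia incidence in Protocol 2.3 as evidence that EPS drives the dropout. It is a pooled adverse event incidence from completed trials, not a discontinuation rate. Protocol 7.3.3 lists adverse events among the reasons for stopping, but no document says how many subjects would stop for EPS. A reader might also infer that the trial's EPS assessment as a whole is misstated. The unaffected summaries above show otherwise.

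**Conclusion.** The mismatch is real and worth correcting, with limited reach. As written, 24 of the 36 by-visit observed-case ANCOVAs rest almost only on early terminators: about 1 per arm per window if the 5% figure is used as an early-termination rate and spread evenly, and about 2 to 6 per arm at assumed rates of 10% to 30%. The counts assume 240 dosed subjects and even or uniform stopping. The conclusion does not depend on the rate: whatever it is, the subjects with data in those windows are those who stopped, and any estimate is a comparison selected after randomisation. The direction and size of any bias cannot be derived from the documents.

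The harm stops at the Week 2, 4, 8 and 10 rows and a minor mixing of ET ratings into Week 6. No primary, key secondary or main EPS summary is affected.

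**What to change.** - **SAP 9.6:** replace the reference to every trial visit with Week 6 and Week 12 for the observed-case ANCOVAs, using only ratings taken at the scheduled Week 6 and Week 12 visits.
- **SAP 10.1:** state that ET and unscheduled SAS, AIMS and BARS ratings are not mapped to any visit window for the by-visit observed-case analyses, Week 6 included. They enter only the last-visit and maximum-value analyses and the BARS severity incidence already planned. The exclusion has to cover all windows: barring ET ratings only where the scales are unscheduled would leave them in Week 6.
- **SAP Section 13:** check that the table list agrees.

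The cost is two sentences of SAP text and 24 fewer models (36 to 12). At 5% early termination the retained rows would still hold roughly 234 subjects at Week 6 (236 less about 2 ET ratings) and 228 completers at Week 12. No data are lost and no trial procedure changes.

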9.7 Suicidality Data

Suicidality is defined as report of at least one occurrence of any type of suicidal ideation or at least one occurrence of any type of suicidal behavior during assessment period (count each person only once).

Treatment emergent suicidal behavior and ideation is summarized by four types: Emergence of suicidal ideation, Emergence of serious suicidal ideation, Worsening of suicidal ideation, Emergence of suicidal behavior.

Emergence of suicidal behavior/ideation is defined as report of any type of suicidal behavior/ideation during treatment when there was no baseline suicidal behavior/ideation.

Emergence of serious suicidal ideation is defined as observation of suicidal ideation severity rating of 4 or 5 during treatment when there was no baseline suicidal ideation.

Worsening of suicidal ideation is defined as a suicidal ideation severity rating that is more severe than it was at baseline.

9.8 Concomitant Medications

Number and proportion of patients taking concomitant medications prior to study therapy, during the double-blind treatment period and after study therapy are tabulated by drug classification using the WHO drug dictionary.

9.9 Extent of Exposure

The start date of double-blind treatment period study therapy after randomization - brexpiprazole or placebo - will be the first day of double-blind treatment period dosing after randomization. The number and percentage of patients who receive double-blind treatment period study medication, will be presented by week and by treatment group. Each dosing week will be based on the actual week; i.e., Day 1-7 in Week 1, Day 8-14 in Week 2, etc. This summary will be performed on the Safety Sample.

The mean daily dosage will be summarized by week and treatment group using descriptive statistics. The mean daily dosage per patient per week will be determined for each week of the study. This will be calculated by dividing the sum of individual total doses by the number of days in the week interval. The summary will contain for each treatment group the number of patients receiving double-blind study medication`, and the mean and range of the mean daily dose for each week.

10 Conventions

10.1 Study Visit Windows

Study visit windows will be used to map visits using study day intervals. Observations at each scheduled visit and Early Termination will be assigned to Week 1, Week 2, Week 4, Week 6, Week 8, Week 10 and Week 12 visits based on their visit windows as shown in Table 10.1A. This visit window convention applies to tables and listings for all efficacy and safety scales (ZAN-BPD, CGI-S, CGI-I, PGI-S, PGI-C, SAS, AIMS and BARS). This derived study window variable will be named as DAY and will be footnoted. In listings, it will be listed along with the CRF study visit.

Table 10.1A shows classifications for study day intervals in the double-blind period. The variable "target day" is defined using the number of days since the start of double-blind dosing. The first day of double-blind dosing is defined as "Day 1".

If more than one observation falls within a particular study day interval, then the last observation within that interval is used. Evaluations occurring more than 7 days after the last double-blind dosing date will not be mapped into study visit windows, and will be excluded from the analysis.

Table 10.1A: Study Day and Visit Windows

Week	Target Day ^a	Study Day Interval ^a
2	7	2-13
4	21	14-27
6	35	28-41
8	49	42-55
10	63	56-69

12	77	70-84 ^b

^a Relative to the first day of IMP in the double-blind treatment period.

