8.1.1 Primary Estimand

The primary estimand defining the treatment effect of interest in the trial uses the hypothetical strategy specified in the International Conference for Harmonisation (ICH) E9 (R1) Addendum. The objective of the primary analysis is to compare the efficacy of brexpiprazole versus placebo for the treatment of subjects with a diagnosis of BPD. The estimand, or target of estimation, following the hypothetical strategy is the pharmacological effect seen, had no withdrawals occurred. This hypothetical estimand is justifiable in this case, since the focus is on the pharmacological effect of the drug additional to non-specific effects. Subjects who withdraw from a symptomatic IMP treatment either could have lost their treatment effect, had the subjects not taken any other symptomatic medication after withdrawal, or could have their treatment effect been masked, had the subjects taken other symptomatic medication after withdrawal. This means that any observations taken after subjects stop IMP will most likely not contribute relevant information about the pharmacological effect of the drug. Due to this strategy, the last collected efficacy assessment after premature trial discontinuation will be done only once at the ET Visit. Every effort will be made to complete all of the ET evaluations prior to administering any additional medications for the treatment of BPD or other prohibited medications. In the case of terminal or lost to follow-up events no ET evaluations would be expected, and only scheduled assessments performed before such an event has occurred.

The primary estimand for this trial is defined by the following components:

- Target Population: FAS for Enriched Subjects
- Endpoint: Change from Baseline to Week 10 in the ZAN-BPD total score
- Intercurrent Events: Premature treatment discontinuation
- Measure of Intervention Effect: Difference in endpoint means between Brexpiprazole and Placebo arm.

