10.3 Scales: Rules for Scoring and Handling of Missing Data

10.3.1 ZAN-BPD

The ZAN-BPD is utilized as the primary efficacy assessment of a subject's severity of disease symptoms in patients with BPD. The questions for the ZAN-BPD reflect a 1-week time frame. Each of the 9 criteria for BPD is rated on a 5-point anchored rating scale of 0 to 4. These scores are clustered into 4 sector scores (akin to domains) and a total score. The 3 affective symptoms (anger, moodiness, and emptiness scores) have a sector score range from 0 to 12. The 2 cognitive symptoms (identity disturbance and distrust/suspiciousness/dissociation scores) have a sector score range from 0 to 8. The 2 impulsive symptoms (self-mutilation/suicidality and other forms of impulsivity scores) have a sector range from 0 to 8. The 2 interpersonal symptoms (efforts to avoid abandonment and unstable relationships scores) have a sector score range of 0 to 8. These 4 sector scores add up

b Evaluations occurring more than seven days after the last dosing date of IMP in the double-blind treatment period will be excluded from the efficacy analyses.

[figure not shown]
to provide the overall total score for the ZAN-BPD, which ranges from 0 to 36. The total score is missing if any element comprising toward the total score is missing.

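### SAP 10.1 lets an early-termination score taken after the last dose replace a valid on-treatment Week 10 rating, which conflicts with the estimand in SAP 8.1.1

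*SAP*

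**What the plan says.** SAP 10.1 has three rules that act together:

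- Mapping: "Observations at each scheduled visit and Early Termination will be assigned to" the analysis weeks according to the study-day intervals in Table 10.1A. Week 10 has target Day 63 and interval Days 56-69.
- Ties: "If more than one observation falls within a particular study day interval, then the last observation within that interval is used".
- Exclusion: "Evaluations occurring more than 7 days after the last double-blind dosing date will not be mapped into study visit windows". Footnote b of Table 10.1A repeats the limit for the efficacy analyses: "Evaluations occurring more than seven days after the last dosing date of IMP".

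The convention covers ZAN-BPD (primary), CGI-S (key secondary), CGI-I, PGI-S, PGI-C and the movement scales.

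SAP 8.1.1 sets a hypothetical estimand with premature treatment discontinuation as the intercurrent event. The target is "the pharmacological effect seen, had no withdrawals occurred", and the stated reason is that "any observations taken after subjects stop IMP will most likely not contribute relevant information about the pharmacological effect of the drug". The same section provides that "the last collected efficacy assessment after premature trial discontinuation will be done only once at the ET Visit". It also bases the estimator on observed cases up to discontinuation from the trial and says that all treatment-period data are used.

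**The concern.** A subject who attends Week 10 on treatment and stops before Week 12 has already supplied the endpoint before the intercurrent event. Nothing hypothetical is needed: the on-treatment rating is what 8.1.1 asks for. If the ET visit falls by Day 69 and within 7 days of the last dose, 10.1 discards that rating for a later one of the kind 8.1.1 calls most likely uninformative. Neither section gives the scheduled or on-treatment rating priority.

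The substitution occurs at the primary time point, and all four steps of the testing hierarchy in SAP 8.3 use Week 10. No analysis in SAP 8.1.4 is defined to remove ET ratings made after the last dose. Placebo-based imputation starts from the observed cases and fills only missing values, so it leaves a mapped ET score as it is.

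**Working it through.** **1. Trace of the rules for one subject**

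| Step | Rule | Result |
|---|---|---|
| Week 10 visit Day 63, on treatment | Days 56-69 | in window |
| Last dose Day 65, ET Day 68 | Days 56-69 | in window |
| Time off drug | 68 - 65 = 3 days, not more than 7 | ET score kept |
| Two scores in one window | last one used | Day 68 replaces Day 63 |

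**2. How far off drug the replacing score can be**

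Protocol Table 1.3-1 allows ±2 days, so the Week 10 visit falls on Days 61-65. The last dose is on or after visit day v and the ET is no later than Day 69, so the largest gap is min(7, 69 - v): 7 days for v = 61 or 62, 6 for Day 63, 5 for Day 64 and 4 for Day 65. ZAN-BPD has a 1-week recall (SAP 10.3.1), so a rating 7 days after the last dose describes an essentially off-drug week.

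**3. The plan's own power figure**

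SAP 4: difference 2.6, SD 6.5, 100 per arm, two-sided 0.05, 80% power. A two-sample t-test with standardised difference 2.6/6.5 = 0.40 gives 80.36%. The plan's figure is reproduced.

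**4. Illustration of size**

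Assumptions, none of them given in the documents: ET dates spread evenly over 77 days, Week 10 visit on Day 63, every ET in the window made after the last dose, and the whole effect lost. The ET rate r is set at 5% (the SAP 4 non-evaluable/dropout allowance, borrowed), 16.7% (the SAP 4 margin, 40/240) and 25% (arbitrary).

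- Overwritten: ET on Days 64-69, 6 days, share o = r × 6/77.
- ET fills an otherwise empty Week 10: Days 56-63, 8 days, share c = r × 8/77.
- Difference under the present rule: 2.6 × (1 - o - c).
- Difference with the tie-break changed: 2.6 × (1 - c).

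| r | o | c | Difference, present rule | Power | Difference, tie-break changed | Power | Gain (points) |
|---|---|---|---|---|---|---|---|
| 5% | 0.39% | 0.52% | 2.576 | 79.65% | 2.586 | 79.96% | 0.3 |
| 16.7% | 1.3% | 1.7% | 2.521 | 77.9% | 2.555 | 79.0% | 1.1 |
| 25% | 1.9% | 2.6% | 2.482 | 76.6% | 2.532 | 78.3% | 1.6 |

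At r = 5%, a visit on Day 61 leaves 8 overwriting days (0.52%, gain 0.41 points) and a visit on Day 65 leaves 4 (0.26%, gain 0.21). If only half the effect is lost, the Day 63 gain at 5% is 0.15 points (80.01% to 80.16%).

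**The case against.** **The rule is explicit.** 10.1 says which score is used and when an ET score is dropped, so nothing is undefined. This stands, and it settles the case of an otherwise empty visit. A reader might infer that an ET score standing in as the Week 10 value (for example last dose Day 53, ET Day 57) is also an error. The documents do not support that. 10.1 and footnote b provide for it, and 8.1.1 plans an ET rating, asks that it precede new medication, and takes data up to trial discontinuation. Its remark on post-IMP data is hedged and is not an exclusion rule. But permission to use an ET score does not justify preferring it to an on-treatment rating at the same visit.

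**Few subjects are affected.** Protocol Table 1.3-1, footnote c, asks for the ET visit as soon as possible, and SAP 8.1.1 notes: "In the case of terminal or lost to follow-up events no ET evaluations would be expected". Both reduce the number affected, and this stands. A reader might go further and take the 5% in SAP 4 as a cap. It is an allowance for non-evaluable subjects and dropout in reaching the Full Analysis Set for Enriched Subjects, which requires only one valid post-randomization ZAN-BPD score. It is not an ET rate within that set.

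**The change drops informative ratings.** SAP 8.1.4.1 says dropout for an adverse event or lack of efficacy may be missing not at random, and the changed tie-break leaves such subjects' final rating out of the primary analysis. This is a real trade-off. It applies only where an on-treatment rating in the same window replaces it, and the hypothetical estimand does not target the off-drug score.

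**Delta adjustment may cover it.** Step 3 of that method adds delta to all values after dropout for certain treated subjects and does not expressly limit this to imputed values. Whether a mapped ET score is shifted is unclear, so it cannot be counted as a safeguard.

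**Conclusion.** The point holds for the overwrite case only. Read literally, 10.1 can replace an on-treatment Week 10 ZAN-BPD or CGI-S rating with a score taken up to 7 days after the last dose, and this conflicts with the estimand in 8.1.1.

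The size is small but not bounded by the documents. In the illustration 0.39% to 1.9% of subjects are overwritten and the changed tie-break gains about 0.3 to 1.6 power points. Those figures rest on assumed ET rates of 5% to 25%, even timing, every ET in the window being off drug, and total loss of effect. ET dates clustered just after the Week 10 visit would raise the share; prompt ET visits and partial loss of effect would lower the impact.

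A reader might infer a risk of a false-positive result. That is not supported: lost effect in the brexpiprazole arm pulls the estimate toward no difference. 8.1.1 also mentions masking by other medication, and its direction is not worked out here. The reason to change is agreement with the estimand, not power. Severity: minor.

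**What to change.** In SAP 10.1, add one sentence: when a window holds both a scheduled assessment dated on or before the last double-blind dosing date and a later ET assessment dated after it, the scheduled assessment is used. Apply it to all efficacy scales (ZAN-BPD, CGI-S, CGI-I, PGI-S, PGI-C), so that one subject's Week 10 values come from one visit. Keep the 7-day rule for otherwise empty visits.

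Optionally, add one sensitivity analysis in which ET scores dated after the last dose are set to missing under MAR, and report how many subjects then have no post-baseline value. It should not be primary, because it removes observed last ratings of subjects who leave for an adverse event or lack of efficacy.

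Cost: one sentence, a small change to the visit-mapping program and, if wanted, one extra run. The tie-break loses no Week 10 value; it only selects between two observed scores. The replaced ET ratings can still be listed. Under the assumptions above, the optional run would set about 0.5% of Week 10 values to missing at a 5% ET rate and 2.6% at 25%, plus some ET scores at other visits.
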